Once patient participants completed the informed consent process they were directed to a second PsychData link in order from them to complete a participant demographics form (Appendix B) that further verified their eligibility into the study. Inclusion criteria consisted of greater than 18 years of age, able to read, speak, and write in English, and presence of low back pain for at least 3 months. Exclusion criteria were current pregnancy or active cancer diagnosis. Patient participants were also excluded from the study if at any point during the episode of care they required different medical attention beyond physical therapy and needed to be referred out for medical reasons and had to discontinue their physical therapy prior to achieving goals. Any patient participant that did not receive at least 80% of the treatments from the initial physical therapist participant were excluded from primary data collection. Physical therapist participant inclusion criteria were having a physical therapy license to treat patients and employed at a clinic site approved for the study.

The initial *a priori* was set for a total of 64 patient participants with the primary complaint of chronic low back pain that had lasted a minimum of 3 months prior to initiating the current physical therapy episode of care. The patient were consecutively enrolled in the study at the various clinic sites. An *a priori* achieves 79% power to detect a Pearson correlation of 0.400 using a two-sided hypothesis test with a significance level of 0.05 with an included 20% dropout rate. These results are based on 1000 samples from the bivariate normal distribution under the alternative hypothesis. The number of physical therapist participants was determined by the clinic site enrollment and treating at least one patient participant during the course of the study.

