### **3.3.3 Instruments – Outcome measurement variables**

The outcome measurements chosen for this study assessed the patients' progress during their physical therapy episode of care on various levels. Patient reported outcomes assessed clinical pain and functional progress by utilizing the Oswestry Disability Index 2.0 (ODI), Numeric Pain Rating Scale (NPRS), and a Global Rate of Change Scale (GROC) as these have been shown to be more responsive than physical impairment measurements.

Oswestry Disability Index 2.0: Improvement in function is a key outcome measurement for clinical conditions and the ODI has shown to have some of the best responsiveness when it comes to patients with low back pain. The ODI has been an extensively used measurement tool to evaluate function and how back pain affects an individual's ability to do daily activities. The ODI assesses function in 10 categories (pain intensity, personal care, lifting, walking, sitting, standing, sleeping, sexual activity, social life, and traveling). Version 2.0^135 was utilized for the purposes of this study. Each of the 10 categories has six statements that are scored from 0 to 5, the statement with the least disability is scored a 0 and the greatest disability scored with a 5. If more than one statement is marked, then the highest score is recorded. The overall score (index) is calculated by taking the total points added up for items answered and dividing by the total possible score (number of categories answered x 5). This number is then multiplied by 100 and rounded to a whole number. Overall index scores can be interpreted for

the range of 0-20% for minimal disability, 21-40% for moderate disability, 41-60% for severe disability, 61-80% for crippled, and 81-100% for individuals bed bound or exaggerating their symptoms. (Appendix I)

Numeric Pain Rating Scale: The NPRS is a unidimensional measurement of pain intensity in adults. It consists of an 11-point ordinal scale measuring pain from “0” = no pain to “10” = worst pain imaginable. The respondents were asked to report on current, best and worst pain in the last 24 hours. All three scores (current, best, and worst) were recorded along calculation of the average of all three being reported. This scale has been used across various diagnoses and age ranges. (Appendix J)

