Global Rate of Change scale: The GROC scale, as stated in its name, is global rating of improvement and satisfaction over the course of treatment. It does not measure a specific dimension such as pain or function, but allows the patient to decide what they consider important. The GROC is a commonly used outcome tool in clinical research, especially as it relates to musculoskeletal care. The most common formats of the GROC is typically a 7, 11, or 15 point scale on a number line with 0 in the middle and moving out one integer in the positive and negative numerical direction. The end anchors also contain the negative and positive words of “very much worse” and “very much improved” or “completely better” with “no change” being in the middle at the zero. Evidence shows that scales with 7 or 11 points offer the best mix of patient preference, appropriate discrimination ability, and test-retest reliability. For purposes of this study the recommended 11-point scale was used (-5 = very much worse, 0 = unchanged, 5 = completely recovered). (Appendix K)

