### **3.3.4 Instruments – Demographic collection**

Demographic data was collected on both the patient along with the treating physical therapists involved in providing care. Each patient provided information regarding age, gender, race, and educational level. The patient's birth order was recorded, as first born or only child have been shown to accept treatment more readily and stayed in treatment longer. Questions related to whether the patient had been seen in physical therapy previously, at this specific site, or by this specific therapist was enquired upon during the initial demographics screening. Lastly, the choice of why the patient participant selected physical therapy, the specific clinic, and physical therapist was asked. (Appendix B) Each of the participating physical therapists also completed a demographics form providing their age, gender, race, level of physical therapy education, specialty certifications (if any), and years practicing as a physical therapist.

(Appendix L)

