informed consent, they progressed to additional PsychData questionnaires to be filled out by the patient participant prior to their initial evaluation with their physical therapist. Information collected consisted of: baseline demographic information sheet, General Trust in Physician Scale, Trust in Physician Scale, PCAS, Wake Forest Scale, ODI, and NPRS. The online participant data collection allowed for blinding of the physical therapist throughout the study to the trust measurement scores. Patient participants received normal physical therapy evaluation and treatment as directed by the physical therapist. Upon completion of the initial visit, the patient participant completed the WAI-SR, Trust in Physician Scale, PCAS, and Wake Forest Scale through a second PyschData link. After completion of the second physical therapy visit, the participating physical therapist completed the PT Survey of Patient Connection and Engagement. Patient participants were blinded to the physical therapist's responses on this instrument. Patient participants continued to receive normal physical therapy as directed by the physical therapist working toward discontinuation of the current episode of care. The majority of the physical therapy encounters (80%) needed to have the initial physical therapist directly involved with the care of the patient participant to be eligible for data collection. If less than 80% of the visits have the direct care delivered by someone other than the initial physical therapist, that data was excluded from primary analysis. Upon discontinuation of the current episode of care or the end of 6 months of care, the patient participant completed the Trust in Physician Scale, PCAS, Wake Forrest Scale, WAI-SR, ODI, NPRS, and GROC. The participating physical therapist completed a second PT Survey of Patient Connection and Engagement at the conclusion of care. (Figure 1) Patient participants that complete all three series of forms (pre-initial visit, post-initial visit, and discontinuation episode) were eligible for a total of \$25 in Walmart gift cards to be mailed to an address of their choice.

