### Statistical Analysis Plan (SAP)

All data was coded and entered into SPSS version 27.0 (IBM Corp., Armonk, N.Y., USA) for statistical analysis. Patient participant and physical therapist participant demographic data was reported with means, ranges, and standard deviations. The primary correlational statistics was the Spearman rho to assess the various individual trust measurement scores and changes in scores over time and individual scores with the primary outcome measurements of pain, function, and global change. The individual trust measurement scores, that have not been used in physical therapy, were be analyzed for correlation to WIA-SR, which has been used in physical therapy research, with Spearman's rho. Friedman's analysis of variance looked at changes in individual trust measurement scores over time from pre-initial visit, post-initial visit, and discharge. The non-parametric analysis was used due to the ordinal nature of the outcome variables. The PT Survey of Patient Connection and Engagement was analyzed for correlation with outcomes and the individual trust measurement scales with the Spearman rho. Linear regression analysis was done with the individual trust measurement scales and outcomes variables for predictive modeling of trust and outcomes assessment.

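### The predictive regression names no baseline ODI or NPRS covariate, although both scores are collected, and does not exclude trust scores recorded together with the outcome

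*Combined protocol and SAP*

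**What the plan says.** The Statistical Analysis Plan makes Spearman's rho the primary correlational statistic. It adds a Friedman test of trust over the three visits and then gives regression a single sentence: "Linear regression analysis was done with the individual trust measurement scales and outcomes variables for predictive modeling of trust and outcomes assessment". That sentence names no covariate and no trust visit. For ODI and NPRS it does not say whether the outcome is the discharge score or the change. No other section supplies these details.

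Section 3.3.5 fixes the timing of the data:
- Before the initial evaluation: "baseline demographic information sheet, General Trust in Physician Scale, Trust in Physician Scale, PCAS, Wake Forest Scale, ODI, and NPRS".
- After the initial visit: "the patient participant completed the WAI-SR, Trust in Physician Scale, PCAS, and Wake Forest Scale through a second PyschData link".
- At the end of the episode or at 6 months: "the patient participant completed the Trust in Physician Scale, PCAS, Wake Forrest Scale, WAI-SR, ODI, NPRS, and GROC".

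Section 3.3.3 describes the NPRS scores: "All three scores (current, best, and worst) were recorded along calculation of the average of all three being reported". It describes GROC as a "global rating of improvement and satisfaction over the course of treatment". GROC is collected only at the end, so it has no baseline counterpart and its form is not in doubt.

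**The concern.** The stated aim is predictive modelling, and two features of the data bear on whether a regression can serve it.

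First, discharge ODI and NPRS would be expected to depend on where the patient started. A model without the baseline score answers a legitimate marginal question: do patients with higher trust finish with better scores? It does not show that trust adds anything to baseline severity, which is what most readers will take prediction to mean. If patients with worse disability report lower trust at the outset, the unadjusted coefficient carries part of the baseline difference. Leaving the covariate out can also cost precision in a small study.

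Second, of the three trust measurements, two precede the outcome and one is taken with it. A patient who has recovered may trust the therapist more because of the recovery. A regression on discharge trust cannot separate that from trust leading to recovery, so it should not be presented as prediction. The sentence leaves this predictor open.

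**Working it through.** **The plan's own figure.** Section 3.3.1 plans 64 patients and puts the power at 79%. Its stated basis is: "to detect a Pearson correlation of 0.400 using a two-sided hypothesis test with a significance level of 0.05 with an included 20% dropout rate". Evaluable n = 64 × 0.8 = 51.2, taken as 51. By Fisher's z, power = Φ(atanh(0.4) × √48 − 1.96) = Φ(0.4236 × 6.928 − 1.96) = Φ(0.975) = 83.5%. Simulation with 40,000 samples gives 84.3% for the Pearson test and 79.7% for the Spearman test. The stated 79% is therefore reproduced for the planned Spearman analysis. It concerns one correlation and does not cover the regression.

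**Set-up for the regression.** Let B be the baseline score, T early trust and Y the discharge score, each with unit variance. Let r be the baseline-discharge correlation and b the size of the trust effect. The documents give none of the correlations used below. The value 0.4 is the protocol's design target; the rest are assumptions. Simulations use 40,000 normal datasets per scenario, n = 51 and two-sided alpha 0.05.

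**Power, T unrelated to B.** Take Y = rB − bT + noise. The size of the correlation each model tests is:
- unadjusted (Y on T): b
- change score (Y − B on T): b/√(2 − 2r)
- adjusted (T given B): b/√(1 − r²), at the cost of one degree of freedom

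Example with b = 0.3, r = 0.6: the correlations are 0.300, 0.3/√0.8 = 0.335 and 0.3/√0.64 = 0.375. Fisher's z gives 57%, 68% and 77%. Simulation gives 58%, 68% and 78%.

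Simulated power for b = 0.3:

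| r | Unadjusted | Change score | Baseline-adjusted |
|---|---|---|---|
| 0.2 | 58% | 39% | 59% |
| 0.3 | 58% | 44% | 61% |
| 0.4 | 58% | 50% | 65% |
| 0.5 | 58% | 58% | 71% |
| 0.6 | 58% | 68% | 78% |
| 0.7 | 58% | 81% | 87% |

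At the protocol's target of 0.4, the unadjusted model already has 84%. Adjustment gives 93%, 97% and 99% at r = 0.5, 0.6 and 0.7.

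**No trust effect given baseline.** Take Y = rB + noise and let a be the trust-baseline correlation. The unadjusted model then sees a correlation of ra, and the change-score model one of size |a|√((1 − r)/2). Example with r = 0.6, a = −0.3: the unadjusted correlation is −0.18, and atanh(0.18) × √48 = 1.26, so rejection is about 1 − Φ(1.96 − 1.26) = 24%.

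Rejection at nominal 5% with a = −0.3:

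| r | Unadjusted | Change score | Baseline-adjusted |
|---|---|---|---|
| 0.3 | 10% | 24% | 5% |
| 0.4 | 13% | 21% | 5% |
| 0.5 | 18% | 18% | 5% |
| 0.6 | 24% | 16% | 5% |
| 0.7 | 31% | 13% | 5% |

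At a = −0.1, the unadjusted and change-score models stay between 5% and 8%. At a = 0 all three are at 5%. These rates are errors only against the null that trust adds nothing once baseline is known. They are not errors for the marginal question.

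**The case against.** The strongest reply is that a summary sentence has been read too hard. A reader might infer that the plan prescribes an unadjusted model, or that it uses discharge trust as the predictor. The documents support neither: the sentence is silent on both. An analyst using change scores would also bring baseline in through the outcome. That stands, and it limits the charge to what the plan fails to state. It does not remove the case for adjustment. A change score is not an adjusted analysis: in the scenarios above it loses power against even the unadjusted model when r is below 0.5, and it inflates rejection when trust is correlated with baseline.

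A second reply is that the gain depends on assumed correlations. That also stands. Follow-up can run to 6 months and r may be low; at r = 0.2 to 0.4 adjustment raises 58% only to 59–65%. The effect of 0.3 is not the protocol's either. But in none of these scenarios did adjustment lower power or lift rejection appreciably above 5%.

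A third reply is that Spearman is primary and the study calls itself correlational, so no sample size rests on the regression. This is correct and limits the severity. A reader might infer that the adjusted regressions should displace the Spearman analysis or reduce it to description. Nothing in the plan supports that.

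**Conclusion.** The point holds in limited form. The only analysis labelled predictive names no baseline covariate, although the baseline scores are collected, and does not rule out a predictor recorded with the outcome.

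The size is conditional. At n = 51 and an assumed effect of 0.3, with trust unrelated to baseline, adjustment is worth between 1 and 29 percentage points of power over the unadjusted model as r goes from 0.2 to 0.7. Over a change score it is worth between 6 and 20. With an assumed trust-baseline correlation of −0.3 and r from 0.3 to 0.7, rejection of the baseline-conditional null is about 10–31% unadjusted, 13–24% for change scores and 5% adjusted. With no such correlation there is no inflation.

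A reader might infer that the study's reported associations are wrong, or that they arise because outcome drives trust. The documents do not show which model was fitted or which visit was used, so neither can be concluded. Because the regression is secondary to Spearman, this is a change that should be made. It is not a flaw in the primary analysis.

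**What to change.** 1. For each trust scale, regress discharge ODI and discharge NPRS (the average defined in section 3.3.3) on trust measured before the outcome, with the matching baseline score as covariate. Name one early visit for the main model, for example post-initial-visit, and report the other early visit as a sensitivity analysis. Both precede the outcome; the post-initial measurement also follows contact with the therapist.
2. Regress GROC on the same trust score.
3. Report any regression on discharge trust, or on trust change to discharge, as a concurrent association and not as predictive.
4. Leave the Spearman correlations as the primary analysis, unchanged.
5. The SAP is written in the past tense. If results have been seen, label the adjusted models post hoc.

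The cost is one degree of freedom in each ODI or NPRS model and a few sentences of SAP or report text. No new data are needed.

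### The regression is offered for predictive modelling with no internal validation stated, so fitted R-squared from about 51 patients can overstate prediction in new patients

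*Combined protocol and SAP*

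**What the plan says.** The section Statistical Analysis Plan (SAP) makes Spearman's rho the primary statistic and then adds: "Linear regression analysis was done with the individual trust measurement scales and outcomes variables for predictive modeling of trust and outcomes assessment". That is all it says about the regression. It does not say how many scales enter a model, which visit they come from, whether any are selected, how performance is measured, or whether it is checked outside the patients used for fitting. The rest of the protocol does not fill these gaps.

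Section 3.3.1 sets the sample size: "The initial *a priori* was set for a total of 64 patient participants". The calculation "achieves 79% power to detect a Pearson correlation of 0.400", for a "two-sided hypothesis test with a significance level of 0.05" and "with an included 20% dropout rate". The sample was therefore sized for one correlation, not for a prediction model.

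Sections 3.3.2 and 3.3.5 describe three provider-specific trust scales, each completed before the first visit, after it and at the end of care, and one general trust scale completed before the first visit. That makes up to 3 × 3 + 1 = 10 trust scores per patient.

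**The concern.** Least squares chooses the coefficients that fit the observed patients best, so part of the fitted R-squared is noise that will not recur. The share grows with the number of predictors and shrinks with the number of patients. With about 51 patients and several correlated scales it need not be small. Choosing the best scale or visit from the same data adds to it.

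Because the stated aim is prediction, the relevant measure is performance in patients who did not contribute to the fit. Without a corrected figure, a statement that trust predicts pain, function or global change could rest on an R-squared that new patients would not reproduce.

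**Working it through.** **Analysable sample.** From section 3.3.1: 64 × (1 − 0.20) = 51.2, about 51. In reverse, 51 / 0.80 = 63.75, which rounds up to the stated 64. The stated power also fits this number: simulating 20,000 bivariate normal samples at a correlation of 0.40, a Spearman test at n = 51 has 79.6% power. A Pearson test, which the text names, has about 84% at n = 51. That difference does not affect this point. The exclusions for changed therapist or medical referral could lower n further; the documents do not say by how much.

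**Inputs.** n = 51 is derived as above. True R-squared = 0.400² = 0.16 comes from the planning correlation. The number of predictors p, and any other value of true R-squared, are assumptions shown as a range.

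**Formulas** (ordinary least squares, normal data, no selection; R² is the true value):

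- Expected fitted R-squared ≈ 1 − (1 − R²)(n − p − 1)/(n − 1)
- Expected R-squared in new patients ≈ 1 − (1 − R²)(1 + 1/n)(n − 2)/(n − p − 2)

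**At R² = 0.16, n = 51:**

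- p = 1: fitted 1 − 0.84 × 49/50 = 0.177; new patients 1 − 0.84 × (52/51) × 49/48 = 0.126; ratio 1.4
- p = 3: fitted 1 − 0.84 × 47/50 = 0.210; new patients 1 − 0.84 × (52/51) × 49/46 = 0.088; ratio 2.4
- p = 4: fitted 1 − 0.84 × 46/50 = 0.227; new patients 1 − 0.84 × (52/51) × 49/45 = 0.067; ratio 3.4 (3.3 in simulation)

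**Range over true R-squared, n = 51** (ratio of fitted to new-patient R-squared):

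| True R² | p = 1 | p = 3 | p = 4 |
|---|---|---|---|
| 0.10 | 1.9 | about 7 | new-patient value about 0 |
| 0.16 | 1.4 | 2.4 | 3.3–3.4 |
| 0.25 | 1.2 | 1.6 | 1.8 |
| 0.40 | 1.1 | 1.2 | 1.3 |

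**Joint R-squared above 0.16.** The 0.400 is a correlation for one score. If three scales each correlate 0.40 with outcome and 0.7 with each other (0.7 is an assumption), their joint R-squared is 3 × 0.16 / (1 + 2 × 0.7) = 0.20. Fitted is then 1 − 0.80 × 47/50 = 0.248 and new-patient 1 − 0.80 × (52/51) × 49/46 = 0.131, a ratio of 1.9. For four scales the joint value is 0.64/3.1 = 0.206 and the ratio is about 2.3.

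**One scale per model, best one reported.** Simulation at n = 51, each score with true R-squared 0.16 and correlations between scores of 0.3 to 0.7 (assumed):

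- best of 4: fitted 0.23–0.26 against 0.12 in new patients, ratio 1.9–2.1
- best of 10: fitted 0.26–0.31 against 0.11–0.12, ratio 2.2–2.8

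**If nobody dropped out** (n = 64, true R-squared 0.16): simulated ratios are 1.3, 1.9 and 2.4 for p = 1, 3 and 4.

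**Does a correction recover the right value?** Over 600 simulated data sets at n = 51 and true R-squared 0.16:

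| p | Leave-one-out | Bootstrap-corrected | New patients (formula) |
|---|---|---|---|
| 1 | 0.135 | 0.125 | 0.126 |
| 3 | 0.087 | 0.084 | 0.088 |
| 4 | 0.083 | 0.083 | 0.067 |

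Both lie much closer to the new-patient value than the fitted R-squared does.

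**The case against.** A reader might infer that predictive strength is bound to be overstated two-fold or more. The documents do not support that. The SAP speaks of individual scales, and one scale per model is a natural reading; if that scale and visit were fixed in advance, the factor is about 1.4 at the planning effect. With three or four scales it falls below two once the true R-squared is 0.25. It also depends on the yardstick: against the population value of 0.16, rather than performance in new patients, fitted R-squared is only about 1.3 times too high with three scales (0.210/0.16) and 1.4 with four (0.227/0.16). Since the stated aim is prediction, the new-patient yardstick is the apt one, but the size remains conditional.

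A reader might also infer that the model is judged solely on its fitted R-squared, or that all nine provider-specific scores enter one model. The SAP is silent on how performance is judged, and nothing in it describes a nine-score model. Discharge trust is collected together with the discharge outcomes, which makes such a model less plausible as prediction. Choosing the best scale is not described either; it is a possibility left open, not a planned step. Nor would a positive fitted R-squared with no true relation automatically become a claim: the regression's significance test would limit false positives to its nominal level per model.

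Finally, the study is correlational, the regression is not the primary analysis, and no prediction tool is planned. This limits the weight of the point. It does not remove it, because the SAP itself names prediction as the regression's purpose and states nothing that would support a predictive claim.

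**Conclusion.** The point holds in conditional form. The SAP states a predictive purpose and no internal validation, and about 51 patients are expected for the fit. In every case examined, fitted R-squared exceeds expected performance in new patients, but by an amount the documents do not determine. At a true R-squared of 0.16 it is about 1.4-fold for one pre-fixed scale, 2.4-fold for three and 3.3- to 3.4-fold for four in one model. For three scales it is about 1.9-fold at 0.20 and 1.6-fold at 0.25. Picking the best of several single-scale models raises the single-scale figure to roughly 1.9- to 2.8-fold.

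These sizes assume normal data and ordinary least squares, and the numbers of predictors, the true R-squared and the correlations between scales are assumed. The correction is worth making because it costs little and changes what may be said about prediction.

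**What to change.** In the section Statistical Analysis Plan (SAP), add that each regression reports, beside the fitted R-squared, either a leave-one-out (PRESS) R-squared or a bootstrap optimism-corrected R-squared. The leave-one-out value comes from the residuals e and leverages h of the same fit: 1 − Σ[e/(1 − h)]² / Σ[(y − ȳ) × n/(n − 1)]². If a scale or visit is chosen from the data, repeat that choice inside each resample. Base any statement that trust predicts outcome on the corrected value. Otherwise describe the regression as an association and drop the word predictive.

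Naming the scales and visit used in each model would also let a reader see which of the cases above applies.

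The cost is a few lines of SAP text, a little more computing on the same data, and a less favourable reported R-squared. No extra patients or assessments are needed.
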